12.4.2 Full Analysis Set

The FAS is defined as all subjects who satisfy the following criteria:

- Randomised to treatment
- Received at least 1 dose of investigational product
- Had a non-missing baseline assessment for the weekly mean of the daily 24-hour WI-NRS score

- Had at least 1 post-baseline assessment for the weekly mean of the daily 24-hour WI-NRS score

Subjects in the FAS will be analysed according to their randomised treatment, regardless of the actual treatment received. The FAS will be used to analyse all efficacy endpoints collected during the double-blind period.

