2.2 Study Design

This study is designed to evaluate efficacy and safety of 0.5 µg/kg IV difelikefalin in Chinese subjects with CKD on HD (3 times weekly) and with moderate-to-severe associated pruritus. A dialysis frequency of 3 times a week (versus twice weekly), is prevalent for the dialysis practice in China [14].

IV administration of difelikefalin will occur at the end of HD by using the return HD line or via injection directly into a vein.

This study design (dose, investigational product administration, duration of treatment) is based on Phase 2 and Phase 3 clinical trials with difelikefalin in subjects with CKD-aP on HD conducted by Cara Therapeutics, Inc. previously outside of China (including clinical trials conducted in Japan by licensees of Cara Therapeutics, Inc.).

This study consists of a double-blind, randomised, placebo-controlled, parallel group treatment period, and an optional open-label extension period.

During the double-blind period, subjects will be administered investigational product (difelikefalin or placebo) at the end of each dialysis session for 12 weeks (3 times weekly, 36 times in total). The duration of the double-blind period is enough for the evaluation of the efficacy and safety in comparison with placebo. In a Phase 2 study in Japan (MR13A9-4), the difference between difelikefalin (0.5 µg/kg) and placebo in reducing NRS score increased until Week 3 and remained about constant at later time points (until Week 8). Based on these results, in an ongoing Phase 3 study in Japan, the primary efficacy

endpoint will be evaluated at Week 4; the same approach is used in this study. Twelve-week double-blind treatment is also considered enough for the assessment of difelikefalin safety in comparison with placebo, as adverse reactions occur early during difelikefalin treatment.

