12.8 Efficacy Evaluations

12.8.1 Primary Efficacy Evaluations

The primary efficacy endpoint is defined as the change from baseline in the weekly mean of the daily 24-hour WI-NRS score at Week 4 (Days 23 to 29) of the double-blind period. The FAS will be used as the primary population for the analysis of the primary efficacy endpoint as well as for its sensitivity analysis. The PPS will be used as a secondary population.

The weekly mean of the 24-hour WI-NRS score will be defined as the sum of the daily WI-NRS score reported during a specific week during the double-blind period (e.g., Days 2 to 8, Days 9 to 15, Days 16 to 22, Days 23 to 29) divided by the number of days with non-missing scores for that week. If the daily WI-NRS is missing for >3 days during a specific week, the corresponding weekly mean WI-NRS will be set to missing. The baseline score will be defined as the average of the daily 24-hour WI-NRS scores collected over the run-in period, including pre-randomisation assessments collected on Day 1.

The change from baseline in the weekly mean of the daily 24-hour WI-NRS score at Week 4 (Days 23 to 29) of the double-blind period will be analysed using a MMRM. Missing scores will not be imputed. Assuming that the data are MAR, the estimates of the treatment differences calculated from the MMRM described below are unbiased. The model will contain treatment, week, and treatment-by-week interaction as fixed effects; baseline NRS score, use of prior anti-itch medication and presence of specific medical conditions as covariates.

Repeated measures will include values collected at the end of Weeks 1, 2, 3, and 4.

An unstructured covariance matrix will be used to model the within-subject errors. Should the model fail to converge, a compound symmetric covariance matrix will be used instead.

The Kenward-Roger2 approximation will be used to estimate the denominator degrees of freedom.

Standard descriptive statistics will be reported on the values and changes from baseline at Week 4 of the double-blind period along with the adjusted mean change at Week 4 for each group and its 2-sided 95% CI. The adjusted mean treatment difference in the change between difelikefalin and placebo groups will be estimated at Week 4 of the double-blind period as the simple contrast in the treatment effect. Its 2-sided 95% CI as well as its p-value will be presented

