Multiple imputed data will be generated using the approach described below. Each imputation data will be analysed using the same MMRM model as the one used for the primary efficacy analysis, and the results of the analyses will be combined. Imputation will be performed using all available data collected at each time point between Week 1 and Week 4 of the double-blind period.

- Intermittent missing NRS scores will first be imputed using the Markov Chain Monte Carlo method implemented with the SAS MI procedure, which is appropriate for non-monotonic missing data. Covariates for baseline NRS score, both randomisation stratification factors and all non-missing NRS scores for each week will be included.
- The monotone missing NRS values will then be multiply imputed with the SAS MI procedure using the monotone regression method. Covariates for baseline NRS score, both randomisation stratification factors and all non-missing NRS scores for each week will be included.
- The MNAR option in Proc MI will be used with the visit values and will reference the placebo group for informing the imputation.
- For each stage, should convergence issues occur due to small cell size for the categorical covariates corresponding to strata, those specific covariates will be removed from the model.

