12.8.2 Secondary Efficacy Evaluations

Secondary and other efficacy endpoints will be analysed using the FAS, as the primary population, and PPS, as a secondary population.

Significance level is set at an alpha of 0.05 (2-sided) and no adjustment will be made for testing multiple secondary outcomes. Some significant findings are expected to occur by chance so undue consideration will not be given to any particular significant difference. Moreover, interpretation of the results will be based on patterns of differences and in conjunction with the results of the primary analyses.

The proportion of subjects achieving ≥ 3 -point and ≥ 4 -point improvement, respectively, from baseline with respect to the weekly mean of the daily 24-hour WI-NRS at Week 4, 8 and 12 of the double-blind period will be analysed using a logistic regression model containing terms for treatment group, baseline WI-NRS score, use of prior anti-itch

medication, and presence of specific medical conditions. Missing NRS data will be imputed using a MI approach, assuming that subjects who discontinue double-blind period early would have similar WI-NRS scores as other subjects in their respective treatment arm that have complete data. The observed number and proportion of subjects with ≥ 3 -point and ≥ 4 -point improvement, respectively, among the non-imputed data will be reported along with the imputed data logistic regression model-based estimates of the proportions of responders (as defined above) with their 2-sided 95% CIs, odds ratio as well as 2-sided Wald 95% CIs and p-value. A sensitivity analysis will be performed. The same logistic regression model will be used as the one specified above; the only difference is that subjects who discontinue investigational product early will be considered non-responders. Further details will be specified in the SAP.

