3 ANALYSIS SETS

The open-label safety analysis set (OL-SAF) consists of all subjects who receive at least 1 dose of investigational product in the open-label extension period. Subjects in the OL-SAF are to be analysed according to the actual treatment sequence received during the double-blind and open-label extension periods (i.e. Placebo/Difelikefalin, Difelikefalin/Difelikefalin) and all sequences pooled (i.e. in total for all patients in the OL-SAF). The OL-SAF is to be used to analyse exposure data to difelikefalin, efficacy and all safety endpoints collected during the open-label extension period.

The full analysis set (FAS) is defined as all subjects who satisfy the following criteria:

- Randomised to treatment
- Received at least 1 dose of investigational product
- Had a non-missing baseline assessment for the weekly mean of the daily 24-hour WI-NRS score

The FAS is to be used to analyse protocol deviations during the study. Subjects in the FAS are to be analysed according to the planned treatment sequence received during the double-blind and open-label extension periods (i.e. Placebo/Difelikefalin, Difelikefalin/Difelikefalin) and all sequences pooled (i.e. in total for all patients). Subjects assigned to Placebo or Difelikefalin in the double-blind period that did not enter the open-label extension period are counted under Placebo/Difelikefalin or Difelikefalin/Difelikefalin, respectively.

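### The protocol's full analysis set drops treated subjects with no post-baseline weekly itch score, so the non-responder and placebo-based sensitivity analyses omit the earliest dropouts

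*Protocol*

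**What the plan says.** Protocol 12.4.2, like the synopsis, sets four conditions for the FAS: randomised, at least one dose, a baseline weekly mean WI-NRS, and "Had at least 1 post-baseline assessment for the weekly mean of the daily 24-hour WI-NRS score". It adds: "The FAS will be used to analyse all efficacy endpoints collected during the double-blind period". The per-protocol set (12.4.3) is built on the same criteria, so no double-blind efficacy analysis uses a wider population.

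Protocol 12.8.1 decides when a weekly mean exists: "If the daily WI-NRS is missing for >3 days during a specific week, the corresponding weekly mean WI-NRS will be set to missing". Week 1 is Days 2 to 8. The same section states: "The FAS will be used as the primary population for the analysis of the primary efficacy endpoint as well as for its sensitivity analysis". One of those sensitivity analyses is the placebo-based imputation, for which "The MNAR option in Proc MI will be used with the visit values and will reference the placebo group for informing the imputation".

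Protocol 12.8.2 also uses the FAS for the responder endpoints. In their sensitivity analysis, "subjects who discontinue investigational product early will be considered non-responders".

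The supplied SAP covers only the open-label extension; its introduction places the double-blind analyses in a separate SAP. Its section 3 begins "The full analysis set (FAS) is defined as all subjects who satisfy the following criteria" and lists only the first three conditions. It uses that set only for protocol deviations. Its section 1.2, on changes from the protocol, does not mention the difference.

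**The concern.** The fourth condition is an exclusion made after randomisation that depends on whether outcome data exist, and early loss of outcome data can depend on treatment. The protocol itself justifies the length of the double-blind period by saying, "as adverse reactions occur early during difelikefalin treatment", so unequal early loss is plausible.

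The two analyses affected are the ones that test how far the result depends on dropout. One scores early discontinuation as failure; the other draws missing values from the placebo group. Neither can act on a subject who has already been removed from the set. If early loss differs by arm, both may look more reassuring than they should.

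Separately, one trial has two sets called FAS with different membership, and the SAP does not record the difference.

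**Working it through.** **Plan's own figure.** With a difference of 0.9, an SD of 2.1, two-sided 5% and 90% power (Protocol 12.2), a two-sample t-test needs 116 per group: power is 0.9015 at 116 and 0.8990 at 115. Allowing for 10% dropout, 116 / 0.90 = 128.9, so 129 per group. The plan's figures reproduce, and this point does not change them.

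**Who is excluded.** A weekly mean survives at most 3 missing days out of 7, so it needs 4 scores. A subject who records daily from Day 2 and stops after Day 4 has 3 scores and no Week 1 mean. Doses fall on Days 1, 3 and 5, so this subject has had one or two doses. Later scores seldom help: in follow-up the scale is completed on dialysis days only (Table 1, note 14), normally three times a week.

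**Which analyses are affected.**
- The MMRM imputes nothing, so a subject with no post-baseline value contributes no outcome. Restoring such subjects leaves the estimate essentially unchanged.
- The non-responder rule needs no post-baseline score. It could count these subjects but does not see them.
- The imputation models carry baseline score and both stratification factors, so they could impute these subjects but do not see them either.

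**Size, non-responder analysis.** The documents do not give the number of such subjects. Let a (active) and b (placebo) be the numbers excluded out of 129 per arm, with rates p_A and p_P among those kept. If the excluded subjects count as non-responders, the restored difference is

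p_A × (129 − a)/129 − p_P × (129 − b)/129.

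The rates are illustrative. They are the Week 12 rates of at least 3-point improvement in Protocol 1.2.2.3: 54.0% and 42.2% (global Phase 3 study), and 51.0% and 27.6% (US Phase 3 study).

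| a / b | Global rates: difference (points) | Global rates: crude odds ratio | US rates: difference (points) |
|---|---|---|---|
| 0 / 0 | 11.8 | 1.61 | 23.4 |
| 3 / 1 | 10.9 | 1.55 | 22.4 |
| 6 / 2 | 9.9 | 1.49 | 21.5 |
| 8 / 8 | 11.1 | 1.57 | 21.9 |
| 1 / 3 | 12.4 | 1.65 | 23.6 |

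Example, global rates, 6 / 2: 54.0 × 123/129 = 51.5 and 42.2 × 127/129 = 41.5. The difference is 9.9 before rounding of the two rates.

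The difference rises when p_P × b exceeds p_A × a. With the global rates that means b greater than 54.0/42.2 = 1.28 times a.

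**Plausible upper end.** In the Japanese Phase 2 study MR13A9-4, 4 of 61 subjects at 0.5 µg/kg had treatment discontinued or interrupted for an adverse event at any time (Protocol 1.2.2.2). That is 6.6%, or about 8 of 129. Exclusion here requires loss within days, so 8 is generous.

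**Size, placebo-based imputation.** Take the design difference of −0.9 and give each restored active subject the placebo mean. The difference becomes −0.9 × (129 − a)/129: −0.88 for a = 3, −0.86 for a = 6 and −0.84 for a = 8. The largest shift is 0.9 × 8/129 = 0.056.

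**The case against.** The strongest reply is that the deciding document is missing. The protocol leaves detailed methods, missing-data procedures and further responder details to the SAP, and the double-blind SAP was not supplied. It may already have removed the condition. This stands, so the point is about the protocol as written and is conditional on that SAP.

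A reader might infer from SAP section 3 that the efficacy population has already been corrected. The documents do not support that. The three-criterion set there serves only protocol-deviation tables, where a post-baseline score has little purpose, and extension efficacy uses the open-label safety set. The SAP shows an inconsistent definition and no more.

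A reader might also infer that the exclusion favours difelikefalin. The protocol says that adverse reactions come early. It does not say that they lead to withdrawal, still less within about four days, and section 7.1 says that dizziness, somnolence and similar effects may subside with continued treatment. Six active exclusions would be about 70% of the roughly 8 expected from the Japanese figure, which covers interruptions and any time on treatment. The direction is therefore open.

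Finally, the affected analyses are secondary in weight: one supports endpoints tested without multiplicity adjustment, and the other is one of two sensitivity analyses of the primary endpoint. That limits the consequence. It does not justify excluding subjects whom the planned methods can already handle.

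**Conclusion.** The point holds for the protocol text. The fourth FAS criterion removes the earliest dropouts from the two analyses designed to penalise dropout, and nothing in the planned methods requires it.

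The effect is probably small. On assumed exclusions of 3/1 to 6/2 (active/placebo) and the global study's rates, the responder difference is overstated by about 0.9 to 1.9 points. Equal loss of 8 per arm changes it by 0.7 points, and loss sufficiently greater on placebo reverses the sign. The placebo-based mean difference moves by at most about 0.06 against an assumed −0.9. With no such subjects the effect is zero. These figures rest on assumed counts, on rates borrowed from earlier studies, and on 129 dosed subjects per arm with a baseline score.

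It does not follow that the primary result is compromised, since the MMRM is essentially unchanged. The two FAS definitions are a separate documentation fault, because the SAP neither explains nor lists the difference.

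**What to change.** - Define the double-blind FAS by three conditions: randomised, at least one dose, non-missing baseline weekly mean.
- In the responder sensitivity analysis, count subjects who discontinue early without any post-baseline weekly mean as non-responders.
- In the placebo-based imputation, impute these subjects from baseline score and stratification factors with placebo as reference.
- Report by arm how many treated subjects have no post-baseline weekly mean.
- Use one FAS definition in the protocol and both SAPs, or give the deviations set its own name, and record the change in SAP section 1.2. Check the double-blind SAP first, since it may already do some of this.

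The cost is low but goes beyond wording: the analysed population changes for every double-blind efficacy endpoint and for the per-protocol set, and subjects with no outcome data need a stated imputation rule. Sample size is unaffected. Responder rates may become slightly less favourable.

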12.4.3 Per-Protocol Set

The PPS consists of all subjects who, in addition to the FAS criteria, do not have any major protocol deviations that will be defined and reviewed during the blinded data review meeting prior to unblinding the data. Subjects in the PPS will be analysed according to their randomised treatment, regardless of the actual treatment received. The PPS will be used to analyse efficacy endpoints collected during the double-blind period and will act as supportive analyses.

12.4.4 Open-label Safety Analysis Set

The OL-SAF consists of all subjects who receive at least 1 dose of investigational product in the open-label extension period. Subjects in the OL-SAF will be analysed according to the actual treatment sequence received during the double-blind and open-label extension periods. The OL-SAF will be used to analyse exposure data to difelikefalin, efficacy as well as all safety endpoints collected during the open-label extension period.

12.5 Background and Demographic Characteristics

For the double-blind period, the number of subjects enrolled, randomised, treated, completed, or discontinued from the treatment and from the study, along with the reason for discontinuation, will be summarised by treatment group and overall.

In addition, the number of subjects in each analysis set will be tabulated.

Subject demographics and baseline characteristics will be summarised by treatment group and overall using descriptive statistics; no formal statistical analysis tests will be performed.

Demographic variables to be summarised will include sex, race, age (years) at informed consent as continuous and categorical variable (18 to <65, ≥65 to <85, ≥85 years) and baseline prescription dry body weight (kg). Height will not be collected.

Baseline characteristics of the disease will also be summarised by treatment group and overall and will include variables such as baseline weekly mean of the daily 24-hour WI-NRS score, use/non-use of anti-itch medication, presence/absence of specific medical conditions, aetiology of CKD, duration of pruritus (years), and years on HD.

Medical history data will be coded using MedDRA and summarised by MedDRA SOC, PT, and treatment group. The data will also be listed, including the verbatim Investigator

description of the relevant medical condition, the coded terms (SOC, PT), start date, end date, and whether or not the condition is ongoing.

12.6 Exposure to Investigational Product

For this study, the duration of double-blind period for each individual subject may be up to 12 weeks, for a total of approximately 36 doses of investigational product administered immediately following each dialysis session. Day 1 of the double-blind period will be defined as the day of administration of the first dose of investigational product. The last day of the double-blind period will be defined as the day of the dialysis session immediately following the last injection of investigational product.

Exposure and treatment compliance during the double-blind period will be summarised by treatment group and by the following parameters:

- Duration of double-blind treatment (days)
- Total number of doses actually received
- Total number of dialysis visits logged
- Number of missed doses
- Number of missed dialysis visits
- Number of subjects with extra doses
- Number of subjects with extra dialysis visits
- Compliance (%)

Duration of double-blind treatment (days) = (date of first dialysis after last dose) – (date of first dose) + 1.

Compliance (%) = actual doses/planned doses

If a subject receives additional dialysis during a given week for any reason, an additional dose of investigational product will be administered following dialysis. A maximum of 4 doses per week is allowed. No additional doses will be given for subjects receiving an additional unscheduled ultrafiltration treatment. The number of subjects getting extra doses will be summarised.

12.7 Concomitant Therapy

All medications will be coded using the World Health Organization Drug Dictionary. Counts and percentages of subject use for each concomitant medication will be tabulated separately by study period, by appropriate World Health Organization Drug Dictionary

classifications and by treatment group. Prior medications will be presented in a listing only. Traditional Chinese medicines should also be recorded.

In addition, prior and concomitant antipruritic medications will be summarised separately by study period; summaries will be presented by ingredient rather than by Anatomical Therapeutic Chemical codes.

A prior medication is defined as any medication taken any time with an end date before the date of the first administration of investigational product.

A concomitant medication is defined as any medication/therapy used on or after the date of the first dose administration of investigational product or as any medication/therapy with a missing end date. If missing, the medication will be assumed to be ongoing and considered as concomitant.

12.8 Efficacy Evaluations

12.8.1 Primary Efficacy Evaluations

The primary efficacy endpoint is defined as the change from baseline in the weekly mean of the daily 24-hour WI-NRS score at Week 4 (Days 23 to 29) of the double-blind period. The FAS will be used as the primary population for the analysis of the primary efficacy endpoint as well as for its sensitivity analysis. The PPS will be used as a secondary population.

The weekly mean of the 24-hour WI-NRS score will be defined as the sum of the daily WI-NRS score reported during a specific week during the double-blind period (e.g., Days 2 to 8, Days 9 to 15, Days 16 to 22, Days 23 to 29) divided by the number of days with non-missing scores for that week. If the daily WI-NRS is missing for >3 days during a specific week, the corresponding weekly mean WI-NRS will be set to missing. The baseline score will be defined as the average of the daily 24-hour WI-NRS scores collected over the run-in period, including pre-randomisation assessments collected on Day 1.

The change from baseline in the weekly mean of the daily 24-hour WI-NRS score at Week 4 (Days 23 to 29) of the double-blind period will be analysed using a MMRM. Missing scores will not be imputed. Assuming that the data are MAR, the estimates of the treatment differences calculated from the MMRM described below are unbiased. The model will contain treatment, week, and treatment-by-week interaction as fixed effects; baseline NRS score, use of prior anti-itch medication and presence of specific medical conditions as covariates.

Repeated measures will include values collected at the end of Weeks 1, 2, 3, and 4.

An unstructured covariance matrix will be used to model the within-subject errors. Should the model fail to converge, a compound symmetric covariance matrix will be used instead.

The Kenward-Roger2 approximation will be used to estimate the denominator degrees of freedom.

Standard descriptive statistics will be reported on the values and changes from baseline at Week 4 of the double-blind period along with the adjusted mean change at Week 4 for each group and its 2-sided 95% CI. The adjusted mean treatment difference in the change between difelikefalin and placebo groups will be estimated at Week 4 of the double-blind period as the simple contrast in the treatment effect. Its 2-sided 95% CI as well as its p-value will be presented

Testing of the primary efficacy endpoint will be 2-sided and conducted at the 5% error level. The null hypothesis in this study is that there is no treatment difference in the primary efficacy analysis of the primary endpoint, i.e., the change from baseline in the weekly mean of the daily 24-hour WI-NRS score at Week 4 of the double-blind period. The alternative hypothesis is that subjects randomised to difelikefalin experience significantly less itching compared to subjects randomised to placebo.

In the primary efficacy analysis, missing NRS data will not be imputed.

Sensitivity analyses of the primary efficacy endpoint will be conducted to evaluate the robustness of study results under different assumptions and imputation algorithms.

For both sensitivity analyses described below, the adjusted mean change at Week 4 for each group and its 2-sided 95% CI, the adjusted mean treatment difference in the change between difelikefalin and placebo groups at Week 4 of the double-blind period, its 2-sided 95% CI as well as its p-value will be estimated as in the primary efficacy analysis.

Sensitivity 1: Multiple Imputation (MI) – MMRM

Multiple imputed data will be generated using the approach described below. Each imputation data will be analysed using the same MMRM model as the one used for the primary efficacy analysis, and the results of the analyses will be combined. Imputation will be performed using all available data collected at each time point between Week 1 and Week 4 of the double-blind period.

- Intermittent missing NRS scores will first be imputed using the Markov Chain Monte Carlo method implemented with the SAS MI procedure, which is appropriate for non-monotonic missing data.
- The monotone missing NRS values will then be multiply imputed with the SAS MI procedure using the monotone regression method.

- For each stage, MI will be performed within treatment group with covariates for baseline NRS score, both randomisation stratification factors and all non-missing NRS scores for each week. Should convergence issues occur due to small cell size for the categorical covariates corresponding to strata (at either stage), those specific covariates will be removed from the model.

Sensitivity 2: Placebo MI – MMRM

Multiple imputed data will be generated using the approach described below. Each imputation data will be analysed using the same MMRM model as the one used for the primary efficacy analysis, and the results of the analyses will be combined. Imputation will be performed using all available data collected at each time point between Week 1 and Week 4 of the double-blind period.

- Intermittent missing NRS scores will first be imputed using the Markov Chain Monte Carlo method implemented with the SAS MI procedure, which is appropriate for non-monotonic missing data. Covariates for baseline NRS score, both randomisation stratification factors and all non-missing NRS scores for each week will be included.
- The monotone missing NRS values will then be multiply imputed with the SAS MI procedure using the monotone regression method. Covariates for baseline NRS score, both randomisation stratification factors and all non-missing NRS scores for each week will be included.
- The MNAR option in Proc MI will be used with the visit values and will reference the placebo group for informing the imputation.
- For each stage, should convergence issues occur due to small cell size for the categorical covariates corresponding to strata, those specific covariates will be removed from the model.

